This will be a randomized control trial to study the efficacy of a combined lidocaine and corticosteroid injection on pain, range of motion, and patient reported outcomes versus a corticosteroid injection alone for the treatment of common upper extremity tendinopathies and nerve entrapments that are often treated with a combination of these injectates. Patients will be assigned randomly to a control group (corticosteroid injection alone) or the treatment group (lidocaine plus corticosteroid injection). At the initial injection a 10-point likert scale prior to and after the injection will be administered. The patients will be followed up at 6 weeks after the injection, at which time the Visual Analog Scale for pain (VAS-pain), range of motion (ROM), and patient reported outcome data will be collected and any complications will be noted. Patients will also utilize a pain journal to track VAS-pain over the first 7 post-injection days. We hypothesize that those who receive lidocaine plus corticosteroid injection will be non-inferior in regards to pain, range of motion (ROM), failure of injection requiring surgery, and patient reported outcome scores compared with patients who received corticosteroid injection alone.

Background and Significance:

Tenosynovitis is a common ailment of the upper extremity resulting in pain around the affected joint due to injury to the tendon sheath. One of the most common manifestations of tenosynovitis is trigger finger. Trigger finger is an extremely common pathology encountered by primary care providers and hand surgeons. Reported incidence of 28 cases per 100,000 has been documented [1]. This entity occurs when the contents of the flexor tendon sheath do not fit cleanly

within the sheath, causing friction on movement of the fingers. Progression from a clicking or locking sensation to complete inability to flex or extend the finger (hence the designation “trigger finger”) occurs over the course of the disease. Therefore, triggering may not be initially noted on exam. Pain from this pathology can be experienced at the proximal interphalangeal joint, the metacarpophalangeal joint, or even the palm [2]. Reported increases in rates have been documented in diabetics, cases of repetitive trauma, those with renal and thyroid disease, and individuals with inflammatory conditions [3].

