2. Determine differences in range of motion of the affected joint in the corticosteroid plus lidocaine group as compared to the corticosteroid alone group.
3. Determine differences in patient-reported outcome scores (VAS-pain, qDASH, PRWE, ASES, SF12, EQOL) in the corticosteroid plus lidocaine group as compared to the corticosteroid alone group.
4. Report patient characteristics associated with efficacy of addition of lidocaine to corticosteroid injectate for pain and ROM resolution (type of injury, affected joint, age, BMI, comorbidities, etc.).

Hypotheses:

Hypothesis⁰: Corticosteroid injectate alone will result in statistically significant reduced pain scores as compared to corticosteroid with lidocaine for the treatment of tenosynovitis.

Hypothesis¹: Lidocaine plus corticosteroid injectate will result in equivalent requirements for repeat injection or conversion to surgery as compared with corticosteroid injectate alone for the treatment of tenosynovitis.

Hypothesis²: Lidocaine plus corticosteroid injectate will result in equivalent patient reported outcomes scores as compared to corticosteroid alone for the treatment of tenosynovitis.

Hypothesis³: Lidocaine plus corticosteroid injectate will result in equivocal patient-reported outcome scores, ROM, and pain reduction as compared to corticosteroid alone for the treatment of tenosynovitis.

Study Design

This will be a randomized control trial of a group of patients with upper extremity tenosynovitides treated with either lidocaine plus corticosteroid or corticosteroid injection alone by upper extremity fellowship trained surgeons at Emory University. Patients will be randomly assigned to one of two groups at the time of treatment: 1. Lidocaine Plus Corticosteroid and 2. Corticosteroid Alone. A random allocation sequence, concealed in consecutively numbered, opaque, sealed envelopes, determining active treatment or placebo, will be computer generated. Written-informed consent will be obtained from patients prior to injection.

Patients in the Corticosteroid group will be treated with a 40 mg/mL injection of corticosteroid following sterile preparation. The volume of injectate differs for each tenosynovitis being treated. For example, trigger finger patients in the corticosteroid alone group will receive a 1mL of injectate total (consisting of 1 mL of 40mg/mL triamcinolone).

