Patients in the Corticosteroid and Lidocaine group will be treated with a 40 mg/mL injection of corticosteroid combined with 1% lidocaine. The volume of injectate differs for each tenosynovitis being treated. For example, patients being treated for trigger finger will receive 0.5 mL of 1% lidocaine and 1 mL of 40mg/mL triamcinolone.

Needle size and insertion site of needle differs for each tenosynovitis being treated. For trigger finger specifically, needle injections will be performed with an appropriately sized needle inserted over the A1 pulley at a 45-degree angle. The injection will be done with the same technique for both groups by the attending physician. The medication will be injected extra-synovially in order to make the treatment more reproducible. This method of injection has been supported in previous studies.

Outcome Measures:

- Likert Scale: A 10-point likert scale will be asked before and after injection which has been previously validated in other studies looking at efficacy and pain surrounding injections of the upper extremity.
- Pain Assessment: A pain assessment will be assessed before performing the injection, at the time of injection, and at each subsequent follow up visit. Pain scores will be obtained via the Visual Analog Pain Scale (VAS-pain), which is ranked from 0 (no pain) to 10 (highest amount of pain). Pain will be assessed at rest and active movement of the affected joint. Patient will also be asked to fill out the VAS-pain score twice daily in a pain journal (once in the morning and once at night) each day until post-injection day 7.
- qDASH/PRWE/ASES/SF12/EQOL score: These scores will be administered at each clinic follow up. They will also be administered 6 week after the injectate has been performed.
- Need for subsequent reinjection and surgical operation will be recorded.

These scores, specifically the 10-point likert, will also be assessed before performing the injection, immediately after the injection, and again at the various follow up appointments. During clinic follow up we will monitor for complications.

Inclusion Criteria:

- All adult clinical patients of Emory upper extremity surgeons undergoing injection for treatment of the following who are willing to participate in the study will be included in the study: Tenosynovitis of the upper extremity, including but not limited to, the shoulder, biceps, elbow, wrist, thumb, carpometacarpal, midcarpal, elbow, and small joints of the hand (PIP, DIP, MP).

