- Between the ages of 18 years and 95 years.

- For trigger finger: patients with a diagnosis of stenosing tenosynovitis based on a history of triggering and the presence of tenderness over the A1 pulley upon clinical examination. All patients, based on the Quinnell grading of trigger finger see in the figure below, will be included.

Grade	Clinical findings (during flexion and extension)
0	Normal movement
I	Uneven movement
II	Actively correctable
III	Passively correctable
IV	Fixed deformity

Exclusion Criteria:

- Patients who are minors, vulnerable subjects, or who are not willing to consent to participate in the study.
- Allergies to glucocorticoids, current daily use of glucocorticoids or strong opioids (morphine, fentanyl, hydromorphone, ketobemidone, methadone, nicomorphine, oxycodone, and meperidine), severe diabetic neuropathy of the hand influencing pain perception, rheumatoid arthritis, and neurological or psychiatric diseases, potentially influencing pain perception.
- Subjects who, in the opinion of the investigator, may be non-compliant with study schedules or procedures.

Statistical Analysis:

Data will be stored on an excel spreadsheet. We will collect the name, medical record number, age at time of surgery, ethnicity, gender, BMI, presence of diabetes, Quinnell grading of trigger finger, smoking status, pre-injection VAS-pain, post-injection VAS-pain, 10 point likert scale, complications, and need for repeat injection or surgical release. It is possible that other variables may be added depending on analysis. Each variable will be used as a nominal variable when possible (e.g. smoking status) or a continuous variable if needed (e.g. VAS-pain, patient related outcome scores). For some statistical calculations we may break up the continuous variables in to ranges (e.g. Ages 15-20, 25-30). We will perform statistical analysis using unpaired, 2-tailed Student t test to compare means for normally distributed data, Kruskal-Wallis test to compare medians of non-normally distributed data, and chi-square test to compare proportions. Statistical significance will be interpreted as $P < .05$. Confidence intervals will be calculated with a confidence level of 95%.

Specifically, the 2 groups will be compared using the Mann-Whitney U test to analyze the difference between the post-injection VAS scores. The Wilcoxon sign-rank test will be used to test the difference between the treatment and control group for pain and patient related outcomes.

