The minimally clinically important difference (MCID) varies for each outcome measure. Therefore, for the purposes of a power analysis, we will use the VAS-pain at the time of injection as the primary outcome. A similar study was published in 2017 from Earp *et al.* comparing needle-free jet lidocaine for pre-corticosteroid injection anesthesia with simultaneous lidocaine and corticosteroid injection. Using the results of this study as a metric, for the purposes of our study, to determine a 1-point change in VAS (4.5 to 3.5) with the reported standard deviation of 2 (SEM

was 0.4, with 30 subjects in each group) in the Earp *et al.* study, the number needed to treat to detect a difference between the treatment and placebo group would be 63 [32]. Therefore, we aim for a sample size of 63 patients for each possible tenosynovitis described in the inclusion criteria.

In total, **we plan to enroll 1000 patients total into this study** when combining all possible tenosynovitides encountered at Emory. These outcomes will be feasible to obtain in a reasonable time frame given the high volume of patients treated for tenosynovitis of all types at Emory. Patients will be grouped together for analysis and also broken into subgroups for sub-analysis based on primary diagnosis for injection.

JMP Pro Software or SPSS will be used to analyze the data and perform the statistics.

Risks to participation

Risks to participation include breach of confidentiality from PHI used to conduct the study. Every effort will be used to scrub data when possible and to use subject numbers/unique identifiers when possible.

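### The pooled range-of-motion comparison mixes joints from shoulder to DIP with no common scale and no joint or diagnosis term, which costs power for small differences and leaves the pooled mean difference hard to interpret

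*Combined protocol and SAP*

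**What the plan says.** - **Objective.** Objective 2 reads in part "Determine differences in range of motion of the affected joint in the corticosteroid plus lidocaine group", compared with corticosteroid alone. Hypothesis 3 and the non-inferiority statement in the Precis/Abstract also cover ROM.
- **Timing.** The Precis/Abstract says that at 6 weeks "the Visual Analog Scale for pain (VAS-pain), range of motion (ROM), and patient reported outcome data will be collected". No baseline ROM is described.
- **Joints.** The Inclusion Criteria cover, without limiting themselves to, "the shoulder, biceps, elbow, wrist, thumb, carpometacarpal, midcarpal, elbow, and small joints of the hand (PIP, DIP, MP").
- **Pooling.** The sample-size text under Statistical Analysis says "Patients will be grouped together for analysis and also broken into subgroups for sub-analysis based on primary diagnosis for injection".
- **Tests.** For continuous outcomes, Statistical Analysis gives an "unpaired, 2-tailed Student t test to compare means for normally distributed data", with rank tests otherwise. It names no covariate, stratified test or regression model. Significance is judged by "Statistical significance will be interpreted as $P < .05".
- **Definition of ROM.** No unit, plane of motion, measuring method or reference scale is given. ROM is missing from the Outcome Measures list and from the listed data fields. Treated joint and primary diagnosis are also missing from those fields, although the plan allows variables to be added.

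**The concern.** VAS-pain runs from 0 to 10 in every patient, whichever joint is treated. ROM does not: joints have different normal arcs, and the same absolute change means different things at a finger and at a shoulder. If ROM values from all joints go into one unadjusted two-group test, the variation between joints counts as error.

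Two things are at stake. Power for a ROM difference falls by an amount that depends on the mix of joints. The pooled mean difference is an average over unlike quantities, so a clinician cannot apply it to any particular joint.

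**Working it through.** **1. The plan's own figure.** The only sample-size calculation is for VAS-pain, "to determine a 1-point change in VAS (4.5 to 3.5) with the reported standard deviation of 2". With two-sided alpha 0.05 and 80% power (the power is inferred, since it is not stated):

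n per arm = 2 × (1.960 + 0.842)² × 2² / 1² = 62.8, so 63.

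The figure of 63 is reproduced as a number per arm. It says nothing about ROM, for which the documents give no difference, SD or margin.

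**2. Inputs for ROM.** From the documents: 1000 patients in two arms. Assumed: 1:1 allocation (500 per arm), measurement in degrees, a true difference of 5 degrees at every joint, and these means/SDs: finger 100/15, wrist 70/12, elbow 140/10, shoulder 150/30.

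**3. Formulas.** Total variance = weighted mean of the within-joint variances (W) + weighted variance of the joint means (B). Joint share = B / (B + W). Power = Φ(difference / (SD × √(2/500)) − 1.96). The SD is √(B + W) for the unadjusted test and √W with a joint term.

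**4. Equal mix, in full.**
- W = (225 + 144 + 100 + 900) / 4 = 342.25, so the within-joint SD is 18.5.
- The mean of the joint means is 115. B = (225 + 2025 + 625 + 1225) / 4 = 1025.
- Total SD = √1367.25 = 37.0, and the joint share is 75%.
- Unadjusted: 5 / (36.98 × 0.0632) = 2.14; Φ(2.14 − 1.96) = 57%.
- With a joint term: 5 / (18.5 × 0.0632) = 4.27; Φ(4.27 − 1.96) = 99%.

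**5. Same means and SDs, other mixes.**

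| Finger / wrist / elbow / shoulder (%) | Joint share | Total SD | Within-joint SD | Power, unadjusted | Power, joint term |
|---|---|---|---|---|---|
| 25 / 25 / 25 / 25 | 75% | 37.0 | 18.5 | 57% | 99% |
| 60 / 13.3 / 13.3 / 13.3 | 68% | 29.8 | 17.0 | 75% | 99.7% |
| 70 / 20 / 5 / 5 | 62% | 24.9 | 15.4 | 89% | 99.9% |
| 80 / 15 / 2.5 / 2.5 | 51% | 21.4 | 15.1 | 96% | above 99.9% |

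**6. Effects proportional to each joint's own SD, equal mix.** The mean of the four SDs is 16.75.
- 0.25 SD: pooled difference 0.25 × 16.75 = 4.19 degrees; unadjusted power 43%, against 98% on a within-joint standardised scale.
- 0.5 SD: pooled difference 8.38 degrees; unadjusted power 95%.

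**7. A second set of assumptions.** Here the joint means and mix were varied, with within-joint SD from 10 to 25 and a 5-degree difference.

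| Assumed joints | Joint share | Power, unadjusted |
|---|---|---|
| Wide spread (means 70–165, equal numbers) | 62–91% | 49–65% |
| Hand-heavy mix | 51–87% | 60–82% |
| One region dominating | 42–82% | 68–92% |
| Similar ROM (means 80–95) | 5–24% | 87–100% |

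Power with a joint term was 88.5% at a within-joint SD of 25 and 97.7% or more at 20 or below.

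**8. In general.** The unadjusted test needs 1 / (1 − share) times the patients of the adjusted one, which is 4 times at a share of 75%. For a 0.5 SD effect, unadjusted power is 94% at a share of 80% but 70.5% at 90%.

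**9. Diagnosis subgroups.** Power = Φ(d × √(n/2) − 1.96), with d in within-joint SDs. With 63 per arm it is 80% for d = 0.5 and 29% for d = 0.25. If 63 is the total, it is 51% and 17%.

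**The case against.** The strongest reply is that the sentence that pools patients also plans subgroups by primary diagnosis, and that Objective 4 lists affected joint among the characteristics to be reported for ROM. Interpretable, roughly joint-specific comparisons are therefore already intended. Randomisation also protects the pooled test; in a simulation of one such case the type I error was 4.3%. ROM is secondary, since VAS-pain is the outcome chosen "for the purposes of a power analysis". All this stands. But the subgroups leave the pooled test as it is, and each is powered only for about 0.5 SD even with 63 per arm.

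A reader might infer more than the documents support:

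- **That ROM is planned in degrees.** No unit is stated and no test is assigned to ROM by name. Its pooling follows from the general sentence on grouping patients. An undefined unit still leaves no common scale.
- **That most of the ROM variance is the joint treated, so a real difference is easily missed.** This rests on means and SDs from outside the documents. The joint share ran from about 5% to 91% over the cases tried, and unadjusted power was 89% and 96% in the two most finger-heavy mixes of the first set.
- **That the largest arcs dominate the pooled mean difference.** Each joint's difference is weighted by its number of patients. Large arcs dominate only if the effect grows with the arc or SD.
- **That the noise favours the predicted finding of no ROM difference.** This holds only if a non-significant P value is read as equivalence. The plan also calculates 95% confidence intervals; noise widens them and makes non-inferiority harder to show. The absence of a ROM margin is a separate matter.

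**Conclusion.** The point holds in a limited form. As written, the plan leads to a pooled, unadjusted ROM comparison across unlike joints. The loss is in efficiency and interpretation, not validity: there is no bias and no inflated type I error.

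That the pooled mean difference has no clear clinical meaning does not depend on any assumed figure. The size of the power loss does. On the first set of assumptions, with 500 per arm and a 5-degree difference, unadjusted power is about 57% to 96%, against about 99% or more with a joint term. If the joints had similar ROM, the loss would be small. Differences of about 0.5 within-joint SD would still be found with about 95% power unless the joint share were very high, near 90%. The practical risk is therefore that smaller differences may be missed. Because ROM is secondary and the remedy is cheap, this is a change worth making but not a threat to the primary comparison.

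**What to change.** 1. Add treated joint and primary diagnosis to the data fields, and state for each joint how ROM is measured and in what unit.
2. For the pooled analysis, put ROM on a within-joint scale, for example each value divided by that joint's pooled within-arm SD.
3. Include joint or primary diagnosis as a factor in the pooled ROM model.
4. Report raw ROM units only within a joint, and do not report a pooled mean difference in raw units.

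The analysis change is a few lines of SAP text and code. Defining ROM joint by joint takes more work, but any ROM analysis needs it. The downside is that the pooled effect is in standardised units, so its clinical size must be read from the joint-specific tables.

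### The plan does not say whether the pooled or the per-diagnosis comparison decides the trial, applies P < .05 throughout without multiplicity control, and gives no interaction test for Objective 4

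*Combined protocol and SAP*

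**What the plan says.** The Statistical Analysis section sets one rule for all analyses: "Statistical significance will be interpreted as" P < .05. It lists two-sample and proportion tests, including an "unpaired, 2-tailed Student t test to compare means for normally distributed data", and adds that "the 2 groups will be compared using the Mann-Whitney U test to analyze the difference between the post-injection VAS scores". A Wilcoxon signed-rank test is also named for between-group pain. No adjustment for multiple tests, testing order or exploratory label appears, and no model or interaction term.

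On the primary outcome the same section says: "for the purposes of a power analysis, we will use the VAS-pain at the time of injection as the primary outcome". The target of 63 patients is then set for each diagnosis, within a total of 1000. On the population analysed it says: "Patients will be grouped together for analysis and also broken into subgroups for sub-analysis based on primary diagnosis for injection".

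Objective 4 is to "Report patient characteristics associated with efficacy of addition of lidocaine to corticosteroid injectate", with type of injury, affected joint, age, BMI and comorbidities as examples. Objective 3 lists six patient-reported scores, one of which is VAS-pain itself. The Hypotheses section gives four hypotheses without ranking them. The Inclusion Criteria name 8 distinct sites (10 if PIP, DIP and MP are counted separately) and leave the list open.

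**The concern.** Two different questions are left to the same set of unadjusted tests.

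The first is whether lidocaine changes pain. It can be answered once in the pooled sample, or many times by diagnosis. The plan allows both and ranks neither. Because the sample size is set per diagnosis, and the Background states a separate aim for trigger finger and for de Quervain tenosynovitis, conclusions about single diagnoses appear to be intended. Each extra unadjusted test adds a chance of a false finding.

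The second is whether the effect differs by diagnosis or patient characteristic, which is what Objective 4 asks. A significant result in one diagnosis and a non-significant one in another does not show a difference between them. None of the listed tests compares treatment effects across subgroups. The section also lets variables be added later and continuous variables be cut into ranges, which widens the choice of subgroups.

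**Working it through.** **Inputs from the plan.** Difference 1 point and SD 2 ("to determine a 1-point change in VAS (4.5 to 3.5) with the reported standard deviation of 2"); threshold 0.05; 63 per diagnosis; 1000 in total. **Assumptions.** Two-sided tests throughout (stated only for the t test), 1:1 allocation, 80% power (not stated), and k diagnoses with each patient counted under one, so that the tests are independent.

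**1. The plan's own figure.** n per arm = 2 × (1.960 + 0.842)² × (2/1)² = 62.8, rounded up to 63. The figure reproduces as a number per arm at 80% power. If 63 were the total for a diagnosis (31.5 per arm), power would be about 51%.

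**2. No true effect in any diagnosis, primary outcome only.** The chance of at least one P < .05 in either direction is 1 − 0.95^k. The chance of at least one false result favouring lidocaine is 1 − 0.975^k.

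| k | Either direction | Favouring lidocaine |
|---|---|---|
| 8 | 34% | 18% |
| 10 | 40% | 22% |
| 12 | 46% | 26% |

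At 63 per arm a complete diagnosis needs 126 patients. 1000/126 = 7.9, so 7 can be filled, for which the either-direction figure is 30%. If 63 is a total, 1000/63 = 15.9, so 15 can be filled, giving 54%.

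**3. Secondary outcomes tested within each of 8 diagnoses.** Equally correlated normal test statistics were simulated (50,000 runs). As the within-patient correlation falls from 0.9 to 0, the chance of at least one P < .05 is 44% to 56% with 2 outcomes and 58% to 87% with 5.

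**4. The same 1-point effect in every diagnosis.** At 80% power each, the chance that at least one diagnosis misses P < .05 is 1 − 0.80^8 = 83% for 8, and 1 − 0.80^10 = 89% for 10. A mixture of significant and non-significant diagnoses is thus the expected result even when the effect does not vary.

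**5. Options.** Pooled, about 500 per arm: SE = 2 × √(2/500) = 0.126, so power for 1 point exceeds 99.9% at alpha 0.05. Per diagnosis with Bonferroni for k = 8: alpha = 0.05/8 = 0.00625, critical value 2.734. At 63 per arm SE = 2 × √(2/63) = 0.356, and power = Φ(1/0.356 − 2.734) = 53%, down from 80%. Restoring 80% takes 103 per arm, or 2 × 8 × 103 = 1648 patients.

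**The case against.** The plan is not silent on priorities. It names a primary outcome, gives a test for post-injection VAS, mentions the pooled analysis first, and calls the by-diagnosis work a sub-analysis. A reader might infer that nothing primary is specified at all; the text does not support that. What stands is narrower. The outcome is named only for the power analysis, the sample size built on it is per diagnosis, a second test is listed for between-group pain, and the deciding population is never stated.

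A reader might also infer that a false-positive diagnosis is likely, or that the plan will probably yield a spurious claim for lidocaine. On the primary outcome alone this is not shown. The chance in either direction is below 50% until 14 diagnoses, and two-sided testing halves the per-test error that favours lidocaine. Sixteen diagnoses at 63 each would need 1008 patients, more than the 1000 planned. The error rates also presume no true effect anywhere; where a real difference exists, a significant result is not false.

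Finally, the plan never says that within-subgroup P values will answer Objective 4. The method is simply not given. The criticism is therefore of an omission, not of a stated wrong method.

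**Conclusion.** The concern holds in this limited form. The deciding comparison is undefined, there is no multiplicity control, and no listed analysis can answer Objective 4. Under a global null, the error across diagnoses on the primary outcome is about 34% to 40% for 8 to 10 diagnoses, against a nominal 5%; for false results favouring lidocaine it is 18% to 22%. It is higher if secondary outcomes are tested within each diagnosis. In the other direction, a uniform 1-point effect would look inconsistent across 8 diagnoses about 83% of the time.

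These figures rest on an assumed number of diagnoses, independent patients, 1:1 allocation and, for the last figure, 80% power per diagnosis. They describe tests of difference. The equivalence and non-inferiority hypotheses have no margin, so no error rate can be computed for them. Nothing here shows that a false finding is more likely than not on the primary outcome for the sites actually listed.

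**What to change.** - Name the pooled between-group comparison of VAS-pain at injection as the single confirmatory test at two-sided 0.05. State one test for it, and whether the score is at rest or on movement.
- Fix the diagnosis categories in advance. Fit one model with treatment, diagnosis and their interaction. Report each diagnosis as an estimate with a 95% CI, labelled supportive. At 63 per arm and SD 2 the half-width is about 1.96 × 0.356 = 0.70 points.
- For Objective 4, list the characteristics in advance and assess each with a treatment-by-factor interaction term, keeping continuous variables continuous.
- Report secondary outcomes as supportive estimates with 95% CIs.

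The cost is SAP wording and one model, with no extra patients. The investigators give up stand-alone significance claims for single diagnoses, and the confirmatory result becomes an average over the mix of diagnoses enrolled. Keeping such claims under Holm or Bonferroni is possible but not free: with 8 diagnoses, power at the first step falls from about 80% to about 53% at 63 per arm. It is not recommended as a costless alternative.
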